# Surgery Day 1 (pre-dose):

- Time of start of surgery will be recorded.
- Continuous collection and measurement of blood loss from start of surgery.
- Amount of blood in blood suction unit and swabs, surgical cloths and compresses will be estimated.
- Approximately 60 minutes after the start of cytoreductive PMP surgery, eligibility to take part in the study will be assessed against the intra-operative inclusion criteria:

an intra-operative prediction of clinically relevant bleeding of > 2 L, requiring hemostatic treatment (high risk for the need of fibrinogen supplementation with BT524 or cryoprecipitate) during surgery.

In subjects who do not meet the intra-operative inclusion criteria no IMP administration will take place and no further assessments intra-operatively will be performed. These subjects will be considered as screening failures and will be treated with standard of care.

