## 10.5 Primary Efficacy Analysis

The primary endpoint / efficacy variable is the intra-operative blood loss after decision to treat the subject with IMP until the end of surgery as measured and calculated by amount of blood from the blood suction unit and amount of blood from surgical cloths and compresses.

The primary analysis of this endpoint will test for non-inferiority in the PPS.

The null hypothesis for the primary analysis is that the degree of inferiority of BT524 compared to standard treatment (FFP/cryoprecipitate) is greater than or equal to the non-inferiority margin. The alternative hypothesis is that the degree of inferiority of BT524 compared to FFP/cryoprecipitate is less than the non-inferiority margin.

 $H_0: µ_1 - µ_2 ≥ δ$  $H_1: µ_1 - µ_2 < δ$ 

where

- µ1 = mean intra-operative blood loss after the decision to treat the subject with IMP in the BT524 treatment arm
- µ2 = mean intra-operative blood loss after the decision to treat the subject with IMP in the FFP-/cryoprecipitate-treatment arm
- $\delta$  = non-inferiority margin = 150 mL

The final analysis will be performed using ANCOVA with the intra-operative blood loss after the decision to treat the subject with IMP until the end of surgery as the dependent variable and the predictive blood loss (>1,000 mL to  $\leq$  2,000 mL and > 2,000 mL) as a covariate. The least square means and treatment difference (BT524 versus standard treatment) in least square means will be presented with the corresponding 95% confidence intervals and 2-sided p-value. Non-inferiority will be demonstrated if the upper confidence limit of the 2-sided 95% confidence interval for the difference in the least square means is less than the non-inferiority margin (150 mL).

This analysis will also be performed in the FAS as a sensitivity analysis.

If non-inferiority is demonstrated, then superiority will be assessed in the FAS with superiority demonstrated if the 2-sided p-value is less than 0.05 (i.e., the upper confidence interval is less than 0 mL) using the analysis performed to assess Non-Inferiority.

No imputation for missing values will be applied.

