6.1 Inclusion/Exclusion Criteria

Only subjects meeting all of the following **inclusion criteria** will be considered for study inclusion (will be considered for randomization to study treatment):

- 1. Written informed consent obtained from subjects indicating that they understand the purpose of and procedures required for the study and are willing to participate in it
- 2. Subjects scheduled for elective major spinal or cytoreductive PMP surgery with expected major blood loss
- 3. Male or female, aged \geq 18
- 4. No increased bleeding risk as assessed by standard coagulation tests and medical history
- 5. Intra-operative trigger for treatment
 - a. Subjects undergoing spinal surgery: Intra-operative clinically relevant bleeding of approximately 1 L, requiring hemostatic treatment during surgery.
 - Subjects undergoing cytoreductive PMP surgery: Intra-operative prediction of clinically relevant bleeding of > 2 L (approximately 60 minutes after the start of cytoreductive PMP surgery), requiring hemostatic treatment during surgery.

Subjects having any of the following exclusion criteria, either at screening and/or at baseline will not be included in the study (will not be randomized to study treatment):

- 1. Pregnancy or unreliable contraceptive measures or breast feeding (women only)
- 2. Hypersensitivity to proteins of human origin or known hypersensitivity reactions to components of the IMP
- 3. Participation in another clinical study within 30 days before entering the study or during the study and/or previous participation in this study
- 4. Treatment with any fibrinogen concentrate and/or fibrinogen-containing product within 30 days prior to infusion of BT524
- 5. Employee or direct relative of an employee of the Contract Research Organization, the study site, or Biotest
- 6. Inability or lacking motivation to participate in the study
- 7. Medical condition, laboratory finding (e.g., clinically relevant biochemical or hematological findings outside the normal range), or physical exam finding that in the opinion of the investigator precludes participation
- 8. Presence or history of venous/arterial thrombosis or TEE in the preceding 6 months

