6.4 Randomization

There will be a stratified randomization per surgery type.

Subjects undergoing spine surgery are to be randomized on a 1:1 basis to receive either BT524 or FFP, and subjects undergoing cytoreductive PMP surgery are to be randomized separately on a 1:1 basis to receive either BT524 or cryoprecipitate.

For subjects undergoing spine surgery the randomization will be stratified according to the predictive blood loss: > 1,000 mL to \leq 2,000 mL and > 2,000 mL. The predictive blood loss will be recorded prior surgery.

Randomization of subjects to treatment will occur intra-operatively (predose) when eligibility for the clinical study has been confirmed.

For subjects undergoing spine surgery the following applies:

After an intra-operative blood loss of approximately 1 L, requiring hemostatic treatment (high risk for the need of fibrinogen supplementation with BT524 or FFP) during surgery, the randomization request will be sent to the pharmacy (if applicable). The pharmacy retrieves the randomization code via Interactive Web Response System (IWRS) and provides the prepared IMP to the unblinded anesthesiologist. In case the anesthesiologist retrieves the randomization code via IWRS, the pharmacy will be informed accordingly and can provide the IMP.

For subjects undergoing cytoreductive PMP surgery the following applies:

Randomization of PMP subjects to treatment will occur intra-operatively (pre-dose) when eligibility for the clinical study has been confirmed. Immediately after the prediction of clinically relevant bleeding > 2 L, requiring hemostatic treatment (high risk for the need of fibrinogen supplementation with BT524 or cryoprecipitate) during surgery, the person responsible for randomization will be informed and the randomization request will be sent. The person responsible for randomization retrieves the

randomization code via IWRS and informs the blood bank/pharmacy. BT524 will be delivered to the operating room by the pharmacy. After randomization, BT524 will be prepared in the operating room in accordance with the manufacturer's instructions and administered immediately after reconstitution by the unblinded anesthesiologist.

After randomization, cryoprecipitate will be thawed and prepared for administration by the local blood bank, delivered to the operating room, and administered upon arrival.

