7.3 Predetermined Covariates and Prognostic Factors

In addition to treatment as a prognostic factor, there is a predetermined covariate for subjects undergoing spinal surgery only. The stratification factor predicted blood loss (> 1,000 mL to \leq 2,000 mL and > 2,000 mL) is a covariate for the analysis of the primary efficacy variable and two secondary efficacy variables: amount of RBCs infused after IMP, post-operative blood loss in the first 24 hours.

Predicted blood loss will also be used as stratification factor in the analyses of two secondary efficacy variables: proportion of subjects with successful correction of fibrinogen level 15 minutes after start of first IMP administration, proportion of subjects with rebleeds after the end of surgery until Day 8.

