12.5 Efficacy Analyses

12.5.1 Primary Efficacy Parameter

The primary efficacy parameter is the intra-operative blood loss after decision to treat the subject with IMP until the end of surgery as measured and calculated by amount of blood from the blood suction unit and amount of blood from swabs, surgical cloths and compresses.

The primary objective of this study is to demonstrate that BT524 is non-inferior that means not worse than FFP/cryoprecipitate with a non-inferiority margin of 150 mL in reducing intra-operative blood loss by intravenous (IV) administration in subjects with acquired hypofibrinogenemia undergoing elective major spinal or abdominal surgery. The primary analysis of this endpoint is a non-inferiority test in the PPS. The null hypothesis for the primary analysis is that the degree of inferiority of BT524 compared to standard treatment (FFP/cryoprecipitate) is greater than or equal to the non-inferiority margin. The alternative hypothesis is that the degree of inferiority of BT524 compared to standard treatment.

where

- μ 1 = mean intra-operative blood loss after the decision to treat the subject with IMP in the BT524 treatment arm
- μ2 = mean intra-operative blood loss after the decision to treat the subject with IMP in the FFP/cryoprecipitate treatment arm
- δ = non-inferiority margin = 150 mL

The final analysis will be performed using a two-way analysis of variance (ANOVA) with the intra-operative blood loss after the decision to treat the subject with IMP until the end of surgery as the dependent variable

and the predictive blood loss (> 1,000 mL to \leq 2,000 mL and > 2,000 mL) as a covariate. The least square means and treatment difference (BT524 versus FFP/cryoprecipitate) will be presented with the corresponding 2-sided 95% confidence intervals and p-value. Non-inferiority will be demonstrated if the upper confidence limit of the 95% confidence interval for the difference in the least square means is less than the non-inferiority margin (150 mL). Assumptions for the ANOVA model will be evaluated by diagnostic (e.g., Shapiro-Wilk test for normality) and graphical methods such as residual plots, including distribution of residuals, and Q-Q plots of residuals. The ANOVA assumptions are reviewed during the BDRM and in case the assumptions are not fulfilled, data transformation and alternative methods are discussed (see sections 12.5.1.3 and 12.5.1.4).

In addition, the following analyses will be presented:

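### The primary model leaves out surgery type, which is a randomization stratum, and SAP 7.3 and 12.5.1 disagree on whether the blood-loss covariate covers pseudomyxoma (PMP) subjects

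*SAP*

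**What the plan says.** **Randomization.** SAP 6.4 says "There will be a stratified randomization per surgery type" (Protocol 6.6 agrees) and adds "For subjects undergoing spine surgery the randomization will be stratified according to the predictive blood loss". That makes three strata: spine above 1,000 and up to 2,000 mL, spine above 2,000 mL, and PMP.

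**Primary model.** Protocol 10.5 says "The final analysis will be performed using ANCOVA with the intra-operative blood loss after the decision to treat" as the dependent variable and names two-level predictive blood loss as the covariate. SAP 12.5.1 keeps those terms and calls the model an ANOVA: "The final analysis will be performed using a two-way analysis of variance (ANOVA) with the intra-operative blood loss after the decision to treat". SAP 12.5.1.1 reuses it for superiority. Surgery type appears only in subgroup or repeated analyses (SAP 8.6, 12.5.1.1, 12.5.1.2).

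**Scope of the covariate.** SAP 7.3 says "In addition to treatment as a prognostic factor, there is a predetermined covariate for subjects undergoing spinal surgery only". SAP 12.5.1 applies the covariate to the whole per-protocol set (PPS), spine and PMP together.

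**Timing.** Of the covariate, SAP 6.4 says "The predictive blood loss will be recorded prior surgery". The PMP trigger of more than 2 L is a later, intra-operative judgement. Protocol 7.1 says "Approximately 60 minutes after the start of cytoreductive PMP surgery, eligibility to take part in the study will be assessed".

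**The concern.** Two things are at stake.

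1. **The model cannot be programmed without a guess.** If SAP 7.3 is followed and PMP subjects carry no covariate value, a complete-case ANOVA drops them. If SAP 12.5.1 is followed, each PMP subject needs a level. The 2 L trigger does not supply it, because the covariate is recorded before surgery and the trigger is judged about an hour into it.

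2. **The error term may carry a difference that the design already controls.** Blood loss is counted from the decision to treat, and that moment differs by surgery type. In spine it follows "Intra-operative clinically relevant bleeding of approximately 1 L, requiring hemostatic treatment during surgery"; in PMP it follows a prediction. A gap between the two means is therefore plausible. Randomization balances the arms across surgery types, so the gap adds almost nothing to the true variability of the treatment difference. It does inflate the estimated standard error when surgery type is left out.

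Interim re-estimation could be affected too. SAP 10.0 recalculates the sample size from observed losses and SDs and lists a much higher number as a reason to stop for futility. An SD that contains the gap would overstate the number needed.

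**Working it through.** **Inputs from the documents.** SD 375 mL, margin 150 mL, one-sided 2.5%, 100 per arm (SAP 6.2, Protocol 10.9); 1:1 allocation within each surgery type (SAP 6.4).

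**Assumptions, because the documents are silent.** 40 of 200 subjects are PMP (the minimum for the second interim), all coded above 2,000 mL; half of the 160 spine subjects are above 2,000 mL; SD 375 mL in every stratum; arms balanced within strata; true difference 0. The gap is the PMP mean minus the spine mean: 250, 500 or 1,000 mL. With an overall mean of 500 mL, these correspond to spine/PMP means of 450/700, 400/900 and 300/1,300 mL.

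**Step 1. The plan's own figure.** A noncentral t calculation gives 100 per arm, with power 80.4%. The stated sample size reproduces.

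**Step 2. Residual SD under the planned model.** The level above 2,000 mL holds 40 PMP and 80 spine subjects: a share of 0.6 of the trial, one third of it PMP. The gap adds 0.6 × 1/3 × 2/3 × gap² = 0.1333 × gap² to the residual variance.
- 250 mL: √(140,625 + 8,333) = 386 mL
- 500 mL: √(140,625 + 33,333) = 417 mL
- 1,000 mL: √(140,625 + 133,333) = 523 mL

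**Step 3. Half-width of the 95% interval.** 1.972 × SD × √(2/100) gives 108, 116 and 146 mL, against 105 mL at SD 375.

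**Step 4. Power.** With balanced strata the estimate itself keeps SD 375 × √(2/100) = 53.0 mL. As a hand check, power is close to Φ((150 − half-width)/53.0). At 500 mL this is Φ((150 − 116.3)/53.0) = Φ(0.64), about 74%. The full calculation averages over the residual sum of squares, which is 375² times a noncentral chi-square with 197 df and λ = (40 × 80/120) × gap²/375².

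| Gap (mL) | Power, planned model | Power, three strata | n per arm for 80%, planned model | n per arm a t-test would request from the residual SD |
|---|---|---|---|---|
| 250 | 78.7% | 80.4% | 104 | 105 |
| 500 | 73.6% | 80.4% | 116 | 123 |
| 1,000 | 52.7% | 80.4% | 162 | 193 |

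Power falls below 75% at a gap of about 450 mL. Simulation with 20,000 trials per case gives 78.2%, 74.0% and 52.8% for the planned model and 80 to 81% with three strata. The SD of the estimate is about 53 mL under both models and its mean is within 1 mL of the truth.

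**Step 5. Type I error at a true difference of 150 mL (40,000 trials).** Planned model 2.0%, 1.5% and 0.3%; three strata 2.4 to 2.6%. The test is conservative.

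**Step 6. Sensitivity at a 500 mL gap.**
- Spine share above 2,000 mL of 0, 50 or 100%: 80, 74 or 72%. At 0% the covariate is the same as surgery type and nothing is lost.
- PMP numbers of 40, 60 or 80: 74, 72 or 72%.
- PMP coded above 2,000 mL in none, half or all: between 71 and 74%.
- PMP SD of 300, 375, 500, 600 or 750 mL: planned 76, 74, 67, 63 or 55%; three strata 83, 80, 75, 69 or 61%. The gain is about 6 to 7 points before rounding, but 80% is reached only if the PMP SD is about 375 mL or less.

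**Step 7. The other reading of 375 mL.** If 375 mL is the total SD of the pooled arms, the within-stratum SD is √(375² − 0.2 × 0.8 × gap²), which is 361 mL at a 250 mL gap and 317 mL at 500 mL. Planned power is then 81.5% and 85.5%, against 83.2% and 91.4% with the strata.

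**Step 8. SAP 7.3 taken literally.** Dropping 40, 60 or 80 PMP subjects leaves 80, 70 or 60 per arm and power of 71, 65 or 58%. The analysis would also be spine-only, although the objective covers abdominal surgery.

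**The case against.** **A PMP subject has a value to code from.** Protocol 7.1 records expected blood loss at the baseline visit, and SAP 12.4 tabulates predictive blood loss by surgery type. This stands, and it makes the coding gap narrower. It does not remove the conflict between SAP 7.3 and 12.5.1, and surgery type is still absent.

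**375 mL may already contain between-stratum variation.** SAP 6.2.1 derived an overall SD from blinded data, and it sizes a plain t-test. If it includes a difference between the two spine strata, the planned covariate recovers part of it. With assumed spine differences of 200, 300 or 400 mL, planned power at a 500 mL gap is about 76, 80 or 86%. This stands as a limit on the size. However, the amendment overview shows the SD being revised in the same protocol version (4.0) that first admitted PMP subjects, which suggests that 375 mL holds no spine-PMP gap.

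**The gap is assumed.** True. At 250 mL the loss is only 1.7 points and 3 mL of half-width.

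**The SAP has fallbacks.** SAP 12.5.1.3 and 12.5.1.4 move to a log transformation or the van Elteren test if normality fails. At a 1,000 mL gap a Shapiro-Wilk test at 5% rejects in about 44% of trials, so the most extreme power figures may not describe the analysis finally run. But neither fallback names surgery type as a stratum.

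**Interims.** The first is spine-only and cannot be affected. SAP 10.0 does not say which SD the recalculation uses, so the requested numbers above are illustrative.

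**A late change is not perfectly clean.** The recalculated sample size and the recommendation do reach the sponsor and study team (SAP 10.0), so the reason for the change and who decided it need to be on record.

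**Conclusion.** The concern holds, and the point should be fixed. It is certain that surgery type is missing from the primary model and that the two SAP sections conflict. The direction is also clear: any spine-PMP gap that the covariate misses widens the interval, with no bias and no extra false claims of non-inferiority.

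The size is not known, because it depends on a gap, a PMP SD and a PMP share that the documents do not give. If 375 mL is a within-stratum SD, the cost runs from under 2 points of power at a 250 mL gap to about 7 at 500 mL and 28 at 1,000 mL. If 375 mL is a total SD, power stays above 80% and the plan forgoes about 2 points at 250 mL and 6 at 500 mL. SAP 6.2 had already lowered power from 90% to 80% to accommodate a larger SD, so there is little slack.

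**What to change.** Before database lock:

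- Use the randomization strata (spine above 1,000 to 2,000 mL, spine above 2,000 mL, PMP) as one three-level factor in the primary non-inferiority and superiority models. Use the same factor in the ANOVAs for red blood cells and post-operative blood loss, the Cochran-Mantel-Haenszel tests and the van Elteren test.
- Reword SAP 7.3 and 12.5.1 so that they agree. The three-level factor removes the need to code PMP subjects by predicted loss.
- State whether 375 mL is a within-stratum or a total SD, and use the within-stratum SD in any re-estimation still to come.
- Record the departure from Protocol 10.5 in SAP 4.1 and the study report, with the decision taken by staff blinded to interim results.
- Optionally, repeat the surgery-type estimates in the PPS and add a treatment-by-surgery interaction test.

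The cost is one model degree of freedom and a documented change made after interim analyses that SAP 10.0 describes as past. The same section keeps interim outputs away from the project team, so blinded staff can make the change. No new data are needed.

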12.5.1.1 Assessment of Superiority

If the non-inferiority is demonstrated by the primary analysis, then superiority will be assessed in the FAS and mFAS and repeated for surgery type, sex and race. For superiority analysis, the null hypothesis is that the blood loss in BT524 treatment arm is greater than that in FFP/cryoprecipitate treatment arm. The alternative hypothesis is that the blood loss in BT524 treatment arm is less than that in FFP/cryoprecipitate treatment arm.

H0: $\mu 1 - \mu 2 \ge 0$ H1: $\mu 1 - \mu 2 < 0$ where $\mu 1$ and $\mu 2$ are the same as above.

The same ANOVA model as the non-inferiority analysis will be used. The least square means and difference of least square means will be presented together with the 95% confidence intervals and 2-sided p-value. The superiority of BT524 is demonstrated if the 2-sided p-value is less than 0.05.

12.5.1.2 Sub-Group Analyses: Predicted Blood Loss

In addition to the primary analysis, a subgroup analysis of the primary endpoint will also be performed in the mFAS. Subgroups are predictive blood loss, as well as spinal and abdominal surgery. These subgroups will be further splitted by sex and race.

Primary endpoint will be analyzed using a one-way ANOVA in each subgroup. The least square means and difference of least square means together with 95% confidence intervals and p-values in each subgroup will be presented.

The intra-operative blood loss after decision to treat with IMP will be summarized descriptively overall and for subgroups predictive blood loss and surgery (spinal, abdominal) and will be listed for the FAS. In addition, intra-operative blood loss after decision to treat with IMP will be summarized as continuous data as a box plot for both treatment arms for the mFAS and the PPS and subgroups predictive blood loss and surgery (spinal, abdominal) for the mFAS.

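### The spinal subgroup analysis of blood loss leaves out the predicted-blood-loss stratum, so its interval against FFP may be wider than needed and can differ from the one in SAP 12.5.1.1

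*SAP*

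**What the plan says.** - **Randomisation (SAP 6.4).** "For subjects undergoing spine surgery the randomization will be stratified according to the predictive blood loss", with two levels: above 1,000 up to 2,000 mL, and above 2,000 mL. PMP subjects are randomised separately 1:1, with no blood-loss stratum described. SAP 7.3 names predicted blood loss as the predetermined covariate for spinal subjects only.
- **Primary analysis (SAP 12.5.1).** "The primary analysis of this endpoint is a non-inferiority test in the PPS". The model is a two-way ANOVA with treatment and the two-level predicted blood loss. It is repeated overall in the FAS and mFAS as a sensitivity analysis.
- **Subgroups (SAP 12.5.1.2).** The section sets the analysis population first: "a subgroup analysis of the primary endpoint will also be performed in the mFAS". The groups are the predicted-loss levels and the two surgery types, each split again by sex and race. The model is then given: "Primary endpoint will be analyzed using a one-way ANOVA in each subgroup".
- **Superiority (SAP 12.5.1.1).** If non-inferiority is shown, superiority is assessed in the FAS and mFAS and repeated for surgery type, sex and race. "The same ANOVA model as the non-inferiority analysis will be used".

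The SAP states no power or precision for any subgroup and gives no reason for moving from the two-way to the one-way model. For the PPS, 12.5.1.2 specifies only a box plot of the two arms, not a modelled subgroup estimate.

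**The concern.** A factor that stratifies randomisation normally stays in the model wherever it varies. 12.5.1.2 drops it in the spinal subgroup and its sex and race splits, which is where the SAP itself says the covariate applies. Omitting a balanced prognostic stratum leaves its variation in the residual, so the standard error is too large for the design.

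The surgery-type split matters more than most subgroups. FFP and cryoprecipitate are pooled as one control group (protocol 10.3), so the spinal subgroup is where a reader sees BT524 against FFP alone. If non-inferiority is shown, the spinal mFAS subgroup gets one interval from the two-way model in 12.5.1.1 and another from the one-way model in 12.5.1.2. Nothing says which is the reported subgroup result.

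**Working it through.** **The plan's own figure.** SAP 6.2 gives SD 375 mL, margin 150 mL, one-sided 2.5% and 80% power. By normal approximation, n per arm = 2 × (1.960 + 0.842)² × 375² / 150² = 98.1, rounded up to 99. With the exact noncentral t, power is 0.7997 at 99 and 0.8036 at 100 per arm, so the stated 100 reproduces. The same SD is used below.

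**Inputs not in the documents (assumed).**
- R², the share of blood-loss variance in spine subjects explained by the stratum: 0 to 0.20.
- SD 375 mL within each surgery type.
- mFAS near 220, the randomised number in SAP 6.2.
- PMP subjects 40 to 100 of 220. SAP 10.0 gives only at least 40, at the second interim analysis.

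**Formulas.** The 95% half-width with 1:1 allocation is t(0.975, N − k) × SD × √(4/N), with k = 2 for one-way and k = 3 for two-way. The two-way residual SD is 375 × √(1 − R²). The one-way interval is therefore wider by a factor of about 1/√(1 − R²).

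**Spinal subgroup, N = 160 (60 PMP).** One-way: 1.975 × 375 × √(4/160) = 117.1 mL.

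| R² | Two-way half-width, same set | 1/√(1 − R²) | One-way wider by |
|---|---|---|---|
| 0 | 117.1 mL | 1.000 | 0% |
| 0.05 | 114.1 mL | 1.026 | 2.6% |
| 0.10 | 111.1 mL | 1.054 | 5.4% |
| 0.20 | 104.8 mL | 1.118 | 11.8% |

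With spine N of 180, 140 or 120, the one-way half-width is 110.3, 125.3 or 135.6 mL; the ratios barely change. To put R² in mL: with strata of equal size and total SD 375, the gap between stratum means is 2 × 375 × √R², which is about 168, 237 and 335 mL for R² of 0.05, 0.10 and 0.20.

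**Simulation.** This used stratified 1:1 randomisation, 160 spine subjects split 60/40 between strata, within-stratum SD 375, no treatment effect, and 4,000 runs per setting.

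| Stratum gap | R² | Mean estimate, either model | One-way / two-way width | Coverage, one-way / two-way |
|---|---|---|---|---|
| 0 mL | 0 | 0.4 mL | 1.000 | 94.8% / 94.9% |
| 150 mL | 0.037 | −1.3 mL | 1.019 | 95.1% / 94.7% |
| 300 mL | 0.133 | −0.2 mL | 1.075 | 96.4% / 94.9% |

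The one-way estimate is unbiased, and its interval is conservative when the stratum matters.

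**Where nothing is lost.** In the abdominal subgroup there is no stratum to restore. The half-width, t × 375 × √(4/N), is 240, 194, 167 or 149 mL for N = 40, 60, 80 or 100 under either model. Within a predicted-loss level the factor is constant, so one-way already carries all that the primary model has.

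**The case against.** The strongest reply is that these are supplementary analyses with no margin or decision rule attached. The estimate is unbiased, any error is conservative, and the loss is unknown and probably modest. All of that stands, and it limits the weight of the point. It does not justify leaving the stratum out of the one subgroup for which it was defined.

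A second reply is that the mFAS is larger than the PPS, which offsets the loss. Against a two-way PPS analysis, one-way in the mFAS is wider only if R² exceeds 1 − 200/220, about 9%. The arithmetic is right, but model and analysis set are separate choices. Within the mFAS, the two-way model is at least as precise apart from one degree of freedom.

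Four stronger readings are tempting, and the documents do not support them.
- *A reader might infer that the comparison with cryoprecipitate also loses precision.* PMP randomisation has no blood-loss stratum (6.4), and the covariate is for spinal subjects only (7.3). Wide abdominal intervals come from small numbers.
- *A reader might infer that modelled subgroup results exist only in the mFAS.* 12.5.1.1 also gives FAS results by surgery type, sex and race, though only once non-inferiority is shown. What is true is that none is specified in the PPS.
- *A reader might infer that the subgroups cannot be reconciled with the pooled result.* 12.5.1 repeats the two-way analysis overall in the mFAS, so a same-set pooled estimate exists.
- *A reader might put the widening at 3.5% to 20%,* from √(375² + gap²/4)/375 with gaps of 200 to 500 mL. No gap is given in the documents, and that range leaves out small or zero gaps. With equal strata around the assumed control mean of about 500 mL, a 500 mL gap means stratum means of 250 and 750 mL.

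Preferring an as-randomised set for supplementary subgroups is also defensible, so a PPS repeat is an option rather than a correction.

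**Conclusion.** The point holds for the spinal subgroup and for sex or race splits that contain spine subjects from both strata. There, 12.5.1.2 omits a factor that the SAP uses in the randomisation, the covariate list and the primary model. The cost is an interval 0% to 11.8% wider than the two-way interval in the same set for R² from 0 to 0.20, with no bias. That range rests on the assumed R²; the documents cannot narrow it.

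If non-inferiority is shown, 12.5.1.1 and 12.5.1.2 also give the spinal mFAS subgroup two intervals from two models. With exact balance within strata the point estimates coincide, so the conflict is mainly in the intervals and p-values.

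This is a modest, inexpensive correction. It does not touch the primary non-inferiority decision.

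**What to change.** In SAP 12.5.1.2:

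1. Use the two-way model, treatment plus predicted blood loss, for the spinal subgroup and for any sex or race subgroup that includes spine subjects from both strata.
2. Keep the one-way model within predicted-loss levels, for PMP, and where a nested cell is too small to fit the stratum. State the minimum cell size in advance.
3. State that 12.5.1.1 and 12.5.1.2 use the same model, so that each mFAS subgroup has one estimate and one interval.
4. Optionally, repeat the surgery-type table in the PPS, since no modelled subgroup estimate is specified in the set that decides non-inferiority.

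The cost is a wording change and a rerun with a model already programmed for the primary analysis; no new data are needed. The one downside is that sparse sex or race cells may not support the extra term, which item 2 covers.
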